Study Title	Anapod TM Humi-Therm Heated Humidification System Breathing Circuit versus Bair Hugger TM Warming Blanket for Intraoperative Maintenance of Body Temperature in Pediatric Patients Undergoing Dental Procedures: a Prospective Randomized Non- Inferiority Study
Study Design	Prospective randomized non-inferiority study
Primary Objective	Determine non-inferiority of Anapod [™] Humi-Therm Heated Humidification System Breathing Circuit compared to Bair Hugger [™] Warming Blanket
Secondary Objective(s)	Need for hyperthermic or hypothermic rescue intervention Correlation of 3M SpotOn Temperature Monitoring with rectal temperatures
Research Intervention(s)/ Investigational Agents	Anapod [™] Humi-Therm Heated Humidification System Breathing Circuit and BairHugger [™] Warming System
IND/IDE # (if applicable)	N/A
Investigational Drug Services # (if applicable)	N/A
Study Population	Pediatric patients undergoing dental procedures
Sample Size (number of participants)	256 (128 patients per study arm)
Study Duration for Individual Participants	Duration of one dental procedure (1-6 hours) including recovery period in the postoperative care unit until discharge home or admission to the floor.

1.0 Objectives

Purpose: Temperature management is an important aspect of perioperative care that falls under the purview of the anesthesiologist. Temperature is recognized as one of four primary vital signs and significant deviations from normal values may result in patient harm. General anesthesia disrupts the body's temperature homeostasis by inhibiting temperature regulation mechanisms such as vasoconstriction/-dilation, shivering and behavioral interventions (donning clothes or leaving an area with excessive heat, for example). Anesthetized patient have a tendency to become hypothermic, especially during long surgical procedures. This results from both the redistribution of cooler peripheral temperatures into the cord (due to vasodilation) as well as actual temperature loss to a cold operating room environment (which is maintained at a lower temperature for the comfort of fully gowned surgeons and nurses). In addition, large surgical incisions predispose the patient to hypothermia through evaporation and convection.

Hypothermia is a recognized risk factor that predisposes the patient to an increased metabolic rate, increased oxygen demand, coagulopathies, impaired wound healing, impaired immune function and increased risk of infection. Therefore, maintenance of normal body temperature is an important goal of every general anesthetic - and is a well-accepted quality metric associated with patient care. Because of the greater surface area to volume relationship, children are thought to be a greater risk of intraoperative hypothermia.

The most widely used method of maintaining body temperature during surgery (and a routine at this institution) is by using a forced-air warming blanket (Bair Hugger warming blanket, 3M). Despite its widespread use, the forced-air warming blanket has its limitations. For example, during certain surgical procedures, the location of the surgical field precludes placement of the warming blanket. In addition, the warming blanket often cannot be placed immediately after the induction of anesthesia (when complex patient positioning is required) - leaving the patient exposed to hypothermic conditions for short (10-15min) or long (30-60min) periods of time. There is hence a need for alternative warming systems that could be implemented immediately following anesthetic induction.

Westmed, Inc. has developed an alternative system that utilizes a heated, humidified breathing circuit to regulate a patient's body temperature in the intraoperative setting. This system is active from the moment the trachea is intubated following anesthetic induction, i.e. there are no delays in instituting thermal management.

Our goal is to evaluate the efficacy of the Westmed system vs the Bair Hugger Blanket.

2.0 Background

- Significance of Research Question/Purpose: The Westmed Inc Anapod system used a humidified warming unit that is located within the anesthesia breathing circuit. The manufacturer has supported studies to evaluate the performance of the Anapod Humi-Therm Heated Humidification System Breathing Circuit in adult subjects. But while the system is being used nationwide in pediatric populations, there have been no studies in pediatrics, nor studies evaluating its performance compared to another well-established warming method (i.e. forced-air warming blanket).
- Preliminary Data: The Anapod Humi-Therm Heated Humidification System Breathing Circuit has been evaluated in three studies

Seo et al., Effect of electrically heated humidifier on intraoperative core body temperature decrease in elderly patients: a prospective observational study, Anesthesiology and Pain Medicine 2016; 11: 211-216

Kaneyuki et al., A comparison of the effectiveness of transtracheal heating and humidification system in maintaining body temperature during general anesthesia with low flow gases, Masui. 2001 Jan;50(1):76-9

Bean et al., Active Humidification and Perioperative Temperature Regulation Using a Novel Heated Airway Circuit after Deep Hypothermic Circulatory Arrest, Society for Cardiovascular Surgery Annual Meeting poster, 2017).

All three of these studies demonstrated that the Anapod system was capable of preventing the development of intraoperative hypothermia. However, as noted, there are no studies evaluating the device in the pediatric population, nor have any of the aforementioned studied compared the Anapod system to other warming methods currently in use.

Existing Literature:

See above

3.0 Outcomes

Primary Endpoint/Outcome: Last measured core temperature at conclusion of the procedure (measured with rectal temperature probe) in patients assigned to the two warming systems.

Secondary Endpoint/Outcomes:

The need for hyperthermic or hypothermic rescue (see Section 5.0 for further explanation)

Cummulative degree-minutes above and below 37°C in the two treatment groups (based on both 3M SpotOn and rectal temperatures.

Correlation of intraoperative 3M SpotOn temperature values with rectal temperatures.

4.0 Study Intervention(s)/Investigational Agent(s)

- Description: This study will utilize the Anapod[™] Humi-Therm Heated Humidification System Breathing Circuit from WestMed,and compare its efficacy in maintaining a patient's body temperature with an established warming method (Bair Hugger[™] Warming Blanket).
- Drug/Device Handling: The Anapod[™] Humi-Therm Heated Humidification System Breathing Circuits will be stored in a separate section in the anesthesia equipment room. They will be clearly labeled "research use only, not for routine patient care". Anesthesia aides will set up the breathing circuit for study patients as directed by the study coordinator.

IND/IDE: N/A

Biosafety: N/A

5.0 Procedures Involved

- Study Design: Prospective randomized non-inferiority study comparing Anapod[™] Humi-Therm Heated Humidification System Breathing Circuit versus Bair Hugger[™] Warming Blanket
- Study Procedures: The study participants will be randomized to one of the following temperature management groups:

Group 1.) Anapod[™] Humi-Therm Heated Humidification System Breathing Circuit, with a starting circuit temperature set at the standard 45°C (note, this is temperature at the unit - NOT the temperature of the gas reaching the trachea).

Group 2.) Bair Hugger[™] Warming Blanket with a starting temperature set at HIGH

All aspects of anesthetic care will be as per routine except that a second temperature recording device will be used (3M SpotOnTM Forehead Temperature probe, used routinely in the operating rooms and postoperative recovery areas) in addition to the standard rectal thermister probe. In both groups, both AnapodTM and a BairHuggerTM systems will be placed and ready for use prior to the induction of anesthesia. Randomization will occur immediately after anesthetic induction and endotracheal intubation.

For Group 1.), the BairHuggerTM blanket will be connected a warming unit, but the unit will not be turned on. Patient warming will be provided via the AnapodTM system. In the event that the patient's rectal temperature falls below 35.6°C (96.08F), the BairHuggerTM warming system will be activated ("Hypothermic Rescue"). In the event that rectal temperature increases to a value of \geq 37.5°C (99.5), the Anapod system will be turned off - and the BairHugger turned on with the warming unit set to "ambient" (meaning cool operating room temperature will be blown over the patient ("Hyperthermic Rescue").

For Group 2, the BairHuggerTM unit will be attached to the warming unit and started as soon as possible. In the event that the patient's rectal temperature falls below 35.6°C, the AnapodTM warming system will be activated ("Rescue"). In the event that rectal temperature increases to a value of \geq 37.5°C (99.5°F), the BairHuggerTM warming unit will be set to "ambient" (meaning cool operating room temperature will be blown over the patient ("Hyperthermic Rescue").

All drugs and devices required for participation:

A standard Bairhugger[™] warming unit, an Anapod[™] Humi-Therm Heated Humidification System Breathing Circuit, and two temperature measurement systems (rectal and SpotOn forehead)

- Data to be collected about participants and the source records that will be used to collect those data:
 - From Epic: MRN, Name, Date of birth, Date of procedure, Height, Weight, procedure performed, and procedure duration. Preop Temperature (in preop area), Initial post-induction temperature (both rectal and SpotOn), final rectal and SpotOn temperatures prior to leaving the OR as well as all rectal and SpotOnTM temperatures recorded intraoperatively, first PACU temperature (SpotOn only) Note: patient temperature data are recorded every minute in the Epic Anesthesia system and will be extracted from the record by manual record review.
- Directly Collected (via research Case Report Forms): Warming device set-points, Rescue interventions (time and temperature when the rescue protocols are initiated.
- Individually Identifiable Health Information: See above. PID including name, MRN, and other demographic information including date of procedure will be collected.

HIPPA Agreement: Attached

Use of radiation: None

Use of Center for Magnetic Resonance Research: N/A_

6.0 Data and Specimen Banking

Specimen Banking: N/A

Data Banking: See above for all collected data. See below for data and data form handling

7.0 Sharing of Results with Participants

None

8.0 Study Duration

Individual Subject Participation Duration: For the duration of the dental procedure (typically 1-6 hours), from induction until discharge from the hospital.

Total Study Duration (all Participants): about 2 years

Total Study Duration Including Data Analysis: about 2.5 years

9.0 Study Population

Inclusion Criteria: Pediatric patients (ages 0-18 years) undergoing elective, scheduled dental procedures at Masonic Children's hospital requiring general anesthesia with endotracheal intubation, anticipated to last a minimum of 1hr. Procedures may include dental x-rays, dental exams, dental extractions, dental filling and dental restorations. Eligible procedures may last up to 6hrs or longer.

Vulnerable Populations: Children, Children with developmental delay, Children with behavioral disorders

Exclusion Criteria:

- Parent refusal of consent
- Patient refusal of assent (if applicable)
- Additional procedures (combined procedures) that involve other specialties besides dentists and other parts of the patient's body other than the oral cavity.
- History of diseases associated with temperature dysregulation (active hyperthyroidism, dysautonomia, osteogenesis imperfecta, history of malignant hyperthermia)
- Patients that will not be intubated for the procedure

Screening: Patients will be seen in dental clinic and scheduled for a dental procedure in the operating room. We will inform the dental clinic staff and make flyers available to patient families (flyer attached), which will introduce them to our study. Patients will be identified before the procedure by either the participating anesthesiologists or

research team by review of the posted operating room schedule (specifically by identifying the dental procedure list and the planned procedure). The research assistant responsible for discussing the research and obtaining the consent will call the patient's family the day before the procedure and determine whether they will consider participation. If the family expresses a willingness to consider participation, the research assistant or anesthesiologist will meet with the family on the day of the procedure to obtain consent and answer any additional questions.

VERSION DATE: Version 3, 4/28/2020

10.0 Vulnerable Populations

Vulnerable Populations

- \boxtimes Children
- □ Pregnant women/Fetuses/Neonates

 \Box Prisoners

□ Adults lacking capacity to consent and/or adults with diminished capacity to consent, including, but not limited to, those with acute medical conditions, psychiatric disorders, neurologic disorders, developmental disorders, and behavioral disorders

□ Approached for participation in research during a stressful situation such as emergency room setting, childbirth (labor), etc.

 \Box Disadvantaged in the distribution of social goods and services such as income, housing, or healthcare

Serious health condition for which there are no satisfactory standard treatments
Fear of negative consequences for not participating in the research (e.g.

institutionalization, deportation, disclosure of stigmatizing behavior)

 \Box Any other circumstance/dynamic that could increase vulnerability to coercion or exploitation that might influence consent to research or decision to continue in research

- $\hfill\square$ Undervalued or disenfranchised social group
- \Box Members of the military
- \boxtimes Non-English speakers
- □ Those unable to read (illiterate)
- \Box Employees of the researcher
- \Box Students of the researcher
- \Box None of the above

Adults lacking capacity to consent and/or adults with diminished capacity to consent: None

Additional Safeguards: N/A

12.0 Local Recruitment Methods

Recruitment Process:

Patients/families that are scheduled for procedures and willing to participate are invited to take part in the study. The research team will make attempts to contact the child's parent or guardian prior to the day of the procedure. The research team which also includes dentistry personnel, [name] will try and speak with the patient and their family to consent them for the study at their dental visit prior to the procedure. If they decide to consent the dentistry staff will do so at that time. If they want to learn about the study at this visit and take the consent home for further consideration whether or not to participate, study personnel (from anesthesia) will contact the parents by phone on the day prior to the procedure to discuss their willingness to participate. Formal consent will then be obtained by direct conversation on the day of the procedure.

In addition, we have created a handout about the study to provide families in the dental clinic prior to their child's procedure. The researchers (PI from Anesthesia and study team from anesthesia) will have their contact information available on the brochure. Hopefully, they will have had time to review the handout and the consent so when the research team attempts to contact them before surgery, their questions will be answered. We will review the study again on the day of surgery.

- Source of Participants: Dental surgery patients being performed on the West Bank of the University of Minnesota, Masonic Children's Hospital .
- Identification of Potential Participants: Patients will be identified in dental clinic as far in advance as possible and by daily review of the surgical schedules in Epic.
- Who will make initial contact with potential participants: Again, the Research team members will make attempts by phone to contact the parent or guardian to describe the study prior to the date of the procedure.

Recruitment Materials: Attached in Ethos

Payment: None

13.0 Withdrawal of Participants

- Withdrawal Circumstances: Parents/Patients may withdraw from the study at any point prior to the induction of anesthesia by the principle investigator for any reason. At this point, the parents possibly will not be present (in the OR) and the patient will be unconscious. If this is the case the research team will inform the family immediately.
- Withdrawal Procedures: Group randomization will take place immediately after anesthetic induction. If a parent/patient withdraws after providing consent but prior to the induction of anesthesia and randomization, no further data will be collected (and any data forms started prior to induction will be destroyed).
- Termination Procedures: the Principle investigator has the right to terminate the study at any time during the study.

14.0 Risks to Participants

Foreseeable Risks:

Overall, the proposed study does not carry any identifiable risks for patients beyond those normally encountered with anesthesia and surgery. Both the BairHugger and Anapod systems are approved for clinical use and are being used for their approved and marketed purposes. There is a potential for both devices to result in unintended hyperthermia - but since body temperature is monitored and recorded continuously, and because Rescue Protocols are in place for all patients, body temperatures outside of the desired ranges (\leq 35.6°C and \geq 37.5°C) will be prevented or corrected quickly. NOTE: this attention to close temperature maintenance EXCEEDS what is done during routine care.

The Anapod[™] Humi-Therm Heated Humidification System Breathing Circuit uses warmed, inspired air to warm the patient. It is theoretically possible that the device might malfunction, resulting in excessively warmed inspired gases and airway injury. However, the device has passed extensive safety testing and has built in safety systems (which shut down the warming system if excessive temperatures are noted). The device will be used only in its FDA approved manner according to all manufacturer specifications and directions. To date, no such failures have been reported to the manufacturer.

Reproduction Risks: None

Risks to Others: None

15.0 Potential Benefits to Participants

Potential Benefits: Participation will not have any direct benefit for the subject.

16.0 Data Management

Data Analysis Plan: Describe the data analysis plan, including any statistical procedures.

Our primary outcome variable is the patient's rectal temperature at the end of the surgical procedure. Since this is a continuous and generally normally distributed variable, intergroup comparisons will be via a simple unpaired t-test.

Our primary secondary variable will the incidence of hypothermia and hyperthermic rescue which will be compared between groups via a 2 x 2 Chi-Square Test (or depending on numbers, a Fisher's Exact Test) [Hypo and Hypothermic Rescue, Yes/No for the two groups).

Cummulative degree-minutes below or above our target values are again expected to be a continuous, normally distributed value and hence can be tested by t-test.

The relationships between rectal and Spot-on intraoperative temperatures will be examined by both correlation analysis (linear regression) and via a repeated-measures Bland-Altman method.

Data Integrity: Objective data will be digitally collected from the EMR and extracted by members of the research team. These extracted data, as well as protocol compliance and the incidence of Rescue interventions will be reviewed by the PI or Co-PI each week. A detailed review of all patients collected to date will be conducted in monthly intervals by the PI. Group assignment will be blinded with the data set (Group A vs B) for review purposes - although it is important to note that true blinding of the providers (including on PI and Co PI) is impossible for this procedural study.

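### The lead secondary outcome counts rescue actions by unblinded staff, and no rule says how a rescue without a trigger crossing, or a crossing without rescue, is counted

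*Combined protocol and SAP*

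**What the plan says.** - **Outcome name.** Section 3.0 lists "The need for hyperthermic or hypothermic rescue (see Section 5.0 for further explanation" as a secondary outcome.
- **Analysis.** Section 16.0 makes it the leading secondary variable: "Our primary secondary variable will the incidence of hypothermia and hyperthermic rescue which will be compared between groups", by chi-square or Fisher's exact test. The coding is given as "Hypo and Hypothermic Rescue, Yes/No for the two groups". As printed, this wording leaves the hyperthermic component unclear.
- **Data source.** Section 5.0 takes it from the case report form: "Rescue interventions (time and temperature when the rescue protocols are initiated".
- **Triggers.** Section 5.0 sets numeric rectal triggers. For Group 1, "In the event that the patient's rectal temperature falls below 35.6°C (96.08F), the BairHuggerTM warming system will be activated". The low trigger is the same in Group 2, and the high trigger is 37.5°C or above in both groups.
- **Blinding.** Section 16.0 accepts that "true blinding of the providers (including on PI and Co PI) is impossible for this procedural study".
- **Discretion.** Section 21.0 lets the physician change to the other system if the assigned one is not working optimally. It gives no temperature for this. Research staff are present and changes are documented.
- **Checks.** Section 18.0 has the PI or Co-PI review each patient's Epic record for protocol compliance, in particular rescue at the correct trigger. Section 16.0 adds a weekly review of compliance and rescue incidence, and masks the group as A or B in the data set.
- **Objective record.** Section 5.0 says temperatures are recorded every minute in Epic and that all intraoperative rectal values will be extracted.

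**The concern.** Need for rescue is a property of the child's temperature. Rescue started is a decision by someone who knows the arm. The two agree only if staff act at every crossing and never act without one.

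Section 21.0 permits action without a crossing, so they can part even when the plan is followed exactly. That section also presents the Bair Hugger as standard of care and back-up. Unequal readiness to switch is therefore plausible, though the documents do not show it. High-temperature rescue also takes different effort by arm: two devices are changed in Group 1, one setting in Group 2.

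If readiness to act differs by arm, the yes/no comparison can show a device difference that is not there or hide one that is. At stake is the interpretation of the leading secondary outcome, not the primary outcome.

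**Working it through.** **No figure to reproduce.** The documents give no rescue rate, crossing rate, adherence rate or power for this outcome. The nearest hint is the historical end-of-case IQR in Section 11.0. Read as 36.9-37.3°C, it gives an SD of about 0.4/1.349 = 0.297°C and, for a normal distribution with mean 37.0°C, about 4.6% at or above 37.5°C. That describes past Bair Hugger cases at one time point. It is not an any-time crossing rate in this trial.

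**Inputs.** From the plan: 128 per arm (Section 11.0) and a 2 x 2 chi-square test (Section 16.0). Assumed: a two-sided 5% level without continuity correction, and every rate below.

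**Formula.** Let c be the proportion of children crossing a trigger, s the probability of action given a crossing, and f the probability of an action counted as rescue given no crossing. The recorded rescue rate is

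p = c × s + (1 − c) × f.

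The chance of p < 0.05 comes from exact enumeration of the two binomial counts.

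**A. Equal crossing (c = 15% in both arms), unequal action, f = 0**

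| Action on crossings | Recorded rates | Falsely significant |
|---|---|---|
| 90% vs 80% | 13.5% vs 12.0% | 6.3% |
| 90% vs 70% | 13.5% vs 10.5% | 11.2% |
| 90% vs 50% | 13.5% vs 7.5% | 34.9% |

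For 95% vs 85%, the figure is 5.0-10.1% across crossing rates of 5-40%. Small gaps matter little.

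**B. Equal crossing, all crossings acted on, discretionary switches counted as rescue in one arm only**

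| c | f = 5% of non-crossers | f = 10% of non-crossers |
|---|---|---|
| 5% | 30.3% | 74.9% |
| 10% | 19.2% | 53.4% |
| 20% | 12.0% | 32.3% |

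Example: c = 10%, f = 10% gives 0.10 + 0.90 × 0.10 = 19% recorded against 10%.

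**C. A true difference hidden (crossing 30% vs 15%, f = 0).** Power is 82.8% if every crossing is acted on. If the lower-rate arm has full action and the higher-rate arm acts on only 85%, 70% or 50% of crossings, the recorded rate in the latter is 25.5%, 21% or 15%. Power is then 55.4%, 23.6% or 4.8%.

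**D. Same test on crossings.** With equal crossing rates of 5-40%, the false-positive rate is 4.7-5.1%. This assumes that early action does not itself change whether a child crosses.

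**Boundary.** Section 5.0 starts low-temperature rescue below 35.6°C, while Section 14.0 describes 35.6°C or lower as outside the desired range. A child at exactly 35.6°C is classified differently by the two sections.

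**The case against.** The strongest reply is that the protocol already ties rescue to need. Section 3.0 points to Section 5.0, where the triggers are numeric, identical in both arms and worded as mandatory. If staff comply, rescue given for temperature equals trigger crossed. Every Epic record is checked, compliance is reviewed weekly, the temperature at each rescue is recorded, and research staff are in the room. A crossing without rescue is a protocol failure that this review should find, and an early rescue can be identified. Half of all crossings going unanswered in one arm would be extreme in monitored, audited patients.

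Much of this stands. It makes large action gaps less likely, and the small-gap results show little harm. It does not close the point. No section says that the review recodes the outcome, and the reviewers cannot be truly blinded. Nor does it reach the discretionary switch, which breaches no trigger rule and has no coding rule.

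Degree-minutes are a temperature-based secondary outcome, but they are measured from 37°C (Section 3.0) or from unspecified target values (Section 16.0). They do not count trigger crossings, and rescue itself alters them.

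A reader might infer that ascertainment bias is demonstrated, or that crossings are free of staff influence. The documents support neither. They give no evidence that readiness to act differs by arm, and an early switch can prevent a crossing.

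**Conclusion.** The point holds as a gap in outcome definition with a possible, unquantified bias. The plan names a need, records an action by unblinded staff, permits action outside the triggers, and has no rule for the cases where need and action differ.

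Under the assumed rates, the consequence runs from negligible (about 6% false significance for 90% vs 80% action at 15% crossing) to serious (about 35% for 90% vs 50%, and 12-75% for one-sided discretionary switching). The switching figures apply only if such switches are counted as rescue, which the documents leave open. These are illustrations of sensitivity, not estimates for this trial. The primary outcome's definition and test are not in question here. The change is worth making because it is cheap and the data are already being extracted.

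**What to change.** 1. Define need for rescue from the minute-level rectal record as two separate yes/no outcomes: the child reached the low trigger, and the child reached the high trigger. Count only readings after assigned warming began, and apply a stated artefact screen.
2. Derive both by script without the arm label. Compare each between arms with a risk difference and 95% CI.
3. Report by arm the rescues and discretionary switches with a prior recorded crossing, those without one, and the crossings not followed by rescue. This is needed because early switching can prevent a crossing, so the derived outcome is not fully immune.
4. Correct the Section 16.0 wording so that the low and high components are named unambiguously.
5. Reconcile Sections 5.0 and 14.0 on whether exactly 35.6°C counts. The clinical triggers and actions are otherwise untouched.

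Cost: revised analysis text, an artefact rule fixed in advance, a short script and a little more analysis work. No new data are needed if the start time of assigned warming is recorded. The planned record of device set-points may already supply it, and this should be confirmed.

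### The rescue outcome, read literally, puts too-cold and too-hot rescue into one yes/no table; the two directions should be analysed separately

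*Combined protocol and SAP*

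**What the plan says.** Section 3.0 (Outcomes) lists as a secondary outcome "The need for hyperthermic or hypothermic rescue", and the synopsis table words it in much the same way. Section 16.0 (Data Analysis Plan) makes this the first-ranked secondary outcome: "Our primary secondary variable will the incidence of hypothermia and hyperthermic rescue", "which will be compared between groups via a 2 x 2 Chi-Square Test", with Fisher's exact test as the alternative when numbers are small. A bracket then describes the table: "Hypo and Hypothermic Rescue, Yes/No for the two groups". 

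Section 5.0 defines two distinct events. Hypothermic rescue is triggered by a rectal temperature below 35.6°C and hyperthermic rescue by one of 37.5°C or more, and each has its own response. The case report form records "Rescue interventions (time and temperature when the rescue protocols are initiated". 

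No section plans a test for each direction, a table with more than two outcome levels, or a descriptive split of rescue by direction. No section gives expected rescue rates, a multiplicity rule for rescue, or a rule for a child who has both kinds.

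**The concern.** A single yes/no by two-arm table has one event category. If both rescues go into it, the event is only that the child left the permitted range, and the side is lost. The sides matter here because one rescue means too little heat and the other too much. If one device warms less than the other, its hypothermic rescues should rise and its hyperthermic rescues should fall. The sum then changes by less than either part and may not change at all.

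Two things are at stake. First, a pooled test can report no difference when the devices differ in both directions. Second, a pooled difference is hard to interpret: a weaker warmer with fewer hyperthermic rescues would simply appear to need less rescue. If two tables were intended, the plan does not say so, and pooled or split could be chosen after the data are seen.

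**Working it through.** **Plan's own figure.** There is none to reproduce for rescue. The 256 children (128 per arm) in Section 11.0 are sized on end-of-case temperature. All rescue rates below are assumptions.

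**1. Illustration with assumed counts (128 per arm, no child with both; Anapod vs Bair Hugger)**

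| Table | Anapod | Bair Hugger | Fisher p |
|---|---|---|---|
| Hypothermic rescue | 15 (11.7%) | 2 (1.6%) | 0.0017 |
| Hyperthermic rescue | 4 (3.1%) | 17 (13.3%) | 0.0051 |
| Pooled | 15+4 = 19 (14.8%) | 2+17 = 19 (14.8%) | 1.0 |

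The risk differences are +10.2 and −10.2 percentage points; pooled, the difference is 0.

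**2. Power under assumed rates** (200,000 simulated trials, 128 per arm, uncorrected chi-square, the two rescues mutually exclusive)

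| Anapod hypo/hyper vs Bair Hugger hypo/hyper | Pooled, 0.05 | Hypo, 0.05 | Hyper, 0.05 | Each direction, 0.025 |
|---|---|---|---|---|
| 15%/2% vs 2%/15% | 4.9% | 98% | 98% | 97% |
| 10%/2% vs 2%/10% | 4.9% | 81% | 81% | 71% |
| 12%/5% vs 2%/15% | 4.8% | 92% | 78% | 86% (hypo), 68% (hyper) |

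In each row the pooled rates are equal, so the pooled test rejects only at its type I error rate.

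**3. What the plan's own temperature figures suggest.** Section 11.0 gives a Bair Hugger end-of-case median of 37.0°C and an IQR of 36.9 to 37.3°C. Under normality, SD = 0.4/1.349 = 0.297°C. Using end-of-case temperature as a proxy for rescue at any time in the case:

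- P(hypothermic) = Φ((35.6 − mean)/SD)
- P(hyperthermic) = 1 − Φ((37.5 − mean)/SD)

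Bair Hugger, mean 37.0: (35.6 − 37.0)/0.297 = −4.72, giving about 0.0001%; (37.5 − 37.0)/0.297 = 1.69, giving 4.6%.

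| Assumed Anapod mean | Hypo | Hyper | Pooled, vs 4.6% | Power pooled | Power hyper alone |
|---|---|---|---|---|---|
| 36.7°C | 0.01% | 0.35% | 0.4% | 65% | 65% |
| 36.6°C | 0.04% | 0.12% | 0.2% | 75% | 77% |
| 36.4°C | 0.35% | 0.01% | 0.4% | 65% | 84% |

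Hypothermia contributes at most 0.35 percentage points, so little is offset. Even so, power falls from 84% to 65% at 36.4°C. In every row the pooled result says that Bair Hugger needed more rescue, without showing that nearly all of it was hyperthermic.

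**4. Where dilution becomes large.** It grows with a wider spread or a larger shift.

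- SD 0.857°C is the value at which 128 per arm gives 80% power for the 0.3°C margin at one-sided 0.025: 0.3 × √(128/2)/(1.960 + 0.842) = 0.857. With assumed means of 37.0 (Bair Hugger) and 36.4°C (Anapod), hypothermia is 5.1% vs 17.5% and hyperthermia 28.0% vs 10.0%. Pooled, it is 33.1% vs 27.5%. Power is 17% pooled, against 90% and 96% separately.
- Cancellation is complete when the two means lie symmetrically about the midpoint of the triggers, (35.6 + 37.5)/2 = 36.55°C. At SD 0.297, means of 37.1 and 36.0°C give 8.9% in each arm, all hyperthermic in one and all hypothermic in the other.

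**The case against.** **Pooling is inferred.** A reader might take it as settled that the plan pools. It is not. The bracket names two rescue types, apparently with a slip for 'Hyperthermic', and could mean one table per type. The *or* in Section 3.0 may simply list the kinds of rescue. This stands: pooling is the most literal reading, not a certainty. It does not remove the need for a change, because on the other reading the plan would contain two tests that it never states, with no multiplicity rule.

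**Direction is visible elsewhere.** A reader might infer that no other outcome would show under-warming or overheating. That is wrong. Section 3.0 lists cumulative degree-minutes above and below 37°C on both thermometers, and Section 16.0 tests them. The primary comparison of final temperature also bears on direction. Fitting a normal distribution to each arm of the illustration gives means of about 36.3 and 36.9°C, a gap of about 0.5°C against the 0.3°C margin. Both points stand in part. Rescue itself changes later temperatures, so both measures recover direction incompletely, and neither compares rescue.

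**The illustration is not the likely case.** A reader might infer that the devices will cancel. The documents do not support that: at SD 0.30°C and Anapod means of 36.4 to 36.7°C, hypothermia is near zero. This stands, subject to the end-of-case proxy, which misses rescues earlier in the case.

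**Any rescue is a legitimate composite.** It measures how often the assigned device failed to hold a child in range. Agreed, so it should be kept as a summary. It cannot carry the comparison alone.

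**Conclusion.** The point holds as a cheap improvement to the leading secondary outcome, not as an error that threatens the primary result. Read literally, Section 16.0 puts two opposite failures into one yes/no test; at the least, the wording leaves open which analysis is planned. A pooled test can dilute a difference and cannot attribute one.

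The size depends on rescue rates that the documents do not give. It runs from almost no loss (SD 0.30°C, Anapod mean 36.6 to 36.7°C), through 65% against 84% power at 36.4°C, to complete loss when the two pooled rates coincide. These figures assume normal temperatures, end-of-case values standing in for rescue, and no child with both rescues. Full cancellation is a hypothetical case, not a forecast.

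**What to change.** Replace the rescue paragraph in Section 16.0 with text to this effect:

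*Hypothermic rescue and hyperthermic rescue are analysed as two separate yes/no outcomes. Each is compared between arms in its own 2 x 2 table by chi-square, or by Fisher's exact test if expected counts are small, and reported as a risk difference with 95% CI. A child with both rescues is counted once in each table. The two tests are adjusted by Holm's method (or each is tested at 0.025). Any rescue is reported as a summary, with each child counted once.*

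Correct the bracket to 'Hypo- and Hyperthermic', and word Section 3.0 and the synopsis to match.

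No new data are needed, because the time and temperature of each rescue are already recorded; no trigger or response changes. The cost is two secondary tests instead of one. At 0.025 each, power per direction falls from 98% to 97% for an assumed 15% vs 2% contrast, and from 81% to 71% for 10% vs 2%. Holm's method loses no more than this.
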